7.6 End-of-Treatment Visit

Patients are permitted to continue treatment with regorafenib until disease progression, or the patient is discontinued due to unacceptable toxicity or decision to discontinue treatment by the patient or the study physician.

If treatment is discontinued because of toxicity or any other reason(s) at a treatment visit and no study treatment is administered, that visit may fulfill the End-of-Treatment visit.

After withdrawal from or completion of protocol treatment, patients must be followed for any new AEs for 30 calendar days after the last dose of study drug.

The following end-of-treatment visit procedures will be performed.

- Physical examination, weight, and vital signs
- BP
- ECOG PS

CONFIDENTIAL

STUDY DEVICE: SIR-Spheres®

SCRI INNOVATIONS STUDY NUMBER: GI 189

DATE OF ORIGINAL PROTOCOL: 16 December 2013

Date of Amendment #1: 15 April 2014

Version 2.0

- AE assessment
- Concomitant medication review
- CBC
- CMP
- PT/PTT/INR (for patients receiving Coumadin therapy)
- Disease assessment
 - CT scan of chest, abdomen and pelvis
 - CEA tumor marker

7.7 Follow-Up

7.7.1 Follow-up for Patients Who Discontinue Prior to Disease Progression

Patients discontinuing treatment for any reason other than PD will be monitored for evidence of disease progression. Patients will be followed every 3 months (± 1 month) for up to a maximum of 6 months after the last patient has been enrolled on study for disease progression. Assessments at these visits will be performed as described in Appendix A **Error! Reference source not found.** and Appendix B **Error! Reference source not found.**

7.7.2 Survival Follow-Up

After disease progression is documented, patients will be followed every 3 months (± 1 month) for survival (e.g., date and cause of death) for up to a maximum of 6 months after the last patient has enrolled on study or death whichever comes first. Patients may be contacted during outpatient visits or by telephone.

8. DRUG FORMULATION, AVAILABILITY, ADMINISTRATION, AND TOXICITY INFORMATION

8.1 SIR-Spheres[®] Microspheres

SIR-Spheres microspheres are to be administered in accordance with the terms of its marketing authorization and in accordance with institutional standard of practice. Please refer to the US Package Insert <http://www.sirtex.com/us/clinicians/package-insert> for detailed information on how to prepare and administer SIR-Spheres microspheres.

8.1.1 Labeling, Packaging, and Supply

Each site will procure a supply of SIR-Spheres microspheres, which is commercially available.

All study medications must be kept in a secure place under appropriate storage conditions. Storage conditions for SIR-Spheres microspheres can be found in the relevant US Package Insert. The expiration date on the label must not be exceeded.

CONFIDENTIAL

STUDY DEVICE: SIR-Spheres[®]

SCRI INNOVATIONS STUDY NUMBER: GI 189

DATE OF ORIGINAL PROTOCOL: 16 December 2013

Date of Amendment #1: 15 April 2014

Version 2.0

The Sponsor or its representatives must be granted access on reasonable request to check drug storage, dispensing procedures, and accountability records.

8.1.2 Preparation and Administration of SIR-Spheres® Microspheres

SIR-Spheres microspheres should be prepared and administered in accordance with the terms of its marketing authorization. .

8.1.3 Precautions and Risks Associated with SIR-Spheres® Microspheres

Overall, the incidence of complications after SIR-Spheres microspheres therapy, if patients are selected appropriately and target (i.e. liver) delivery is performed meticulously, is low.

Gastroduodenal complications occur in less than 10% of those treated (Bester et al. 2011; Kennedy et al. 2006; Stubbs et al. 2004) and are largely preventable.

A life-threatening complication, progressive pulmonary insufficiency secondary to radiation-induced lung fibrosis can be avoided by excluding from treatment with SIR-Spheres microspheres any patient with marked hepato-pulmonary shunting (Leung et al. 1995). There have been rare reported occurrences of this complication since that time.

The gallbladder also may receive SIR-Spheres microspheres through a patent cystic artery leading to radiation cholecystitis. In order to avoid this potential complication, infusion distal to the cystic artery is preferred, however the risk of radiation cholecystitis requiring cholecystectomy is low (Liu et al. 2005).

Gastric and duodenal ulceration have been reported to occur after the use of SIR-Spheres microspheres and are related to the inadvertent intestinal deposition of microspheres via extra-hepatic visceral arterial branches. Even in the absence of extra-hepatic activity on 99m Tc labelled MAA and Bremsstrahlung emission images, gastrointestinal symptoms have been reported to develop. The risk of gastrointestinal ulceration can be minimised with routine coil embolization of the extra-hepatic visceral arteries before infusion of SIR-Spheres microspheres (Liu et al. 2005).

Radioembolization induced liver disease (REILD) is a rare complication following selective internal radiation therapy (SIRT) with 90 Y microspheres. REILD is characterised by a well-defined constellation of temporal, clinical, biochemical and histopathologic findings. REILD typically manifests approximately 4-8 weeks post-SIRT and is characterised clinically by jaundice and ascites in the absence of tumour progression or bile duct obstruction. The typical biochemical picture of REILD is an elevated bilirubin (> 3 mg/dL) in almost all cases, elevated ALP and gamma-glutamyl transpeptidase (GGT) in most cases, accompanied by virtually no change in the transaminases (AST and ALT). In the event that a liver biopsy is performed, the typical histological appearance is of sinusoidal obstruction that may resemble veno-occlusive disease.

REILD may occur in both non-cirrhotic and cirrhotic patients. In non-cirrhotic patients, the main risk factors for the development of REILD include prior exposure to systemic chemotherapy and whole-liver SIRT. In cirrhotic patients, the main risk factors are small liver volume (< 1.5 L) and elevated bilirubin (1.2 mg/dL) at baseline. It is relevant to note that REILD is indeed very rare in the setting of an otherwise healthy liver and is largely confined to patients with a well-known

CONFIDENTIAL

STUDY DEVICE: SIR-Spheres®

DATE OF ORIGINAL PROTOCOL: 16 December 2013

Date of Amendment #1: 15 April 2014

SCRI INNOVATIONS STUDY NUMBER: GI 189

Version 2.0

liver condition such as cirrhosis or who have been exposed to any form of potential liver insult, most usually prior chemotherapy. Patients presenting with small liver volumes (< 2.0 L) and low proportional tumour burden (< 0.20) may be at higher risk of developing REILD independent of other factors; appropriate dose recommendations per the study protocol should be strictly adhered to in these cases.

The treatment of REILD may comprise tapering high dose corticosteroids and ursodeoxicolic acid. Low molecular weight heparin may also be considered but both corticosteroids and heparin may only be useful if commenced very early in the course of the disease.

Apart from the above listed major complications² other side effects and complications include:

In approximately one-third of patients, administration of SIRT causes immediate short term abdominal pain requiring narcotic analgesia.

Post SIRT treatment lethargy and mild nausea are common symptoms and can last up to ten days and may require medication.

Most patients develop a mild fever that may last for several days following SIRT administration. This fever does not require treatment.

The most common potential serious complications result from either (1) inadvertent administration of SIR-Spheres microspheres into the gut resulting in gastritis/duodenitis or (2) radiation induced liver disease resulting from a radiation overdose to the normal liver parenchyma. The incidence rate of gastritis/duodenitis can be reduced by experience and meticulous attention to the administration procedure so as to ensure that there is a minimal chance of SIR-Spheres microspheres entering small arteries supplying the gut. Radiation induced liver disease is largely, but not totally, preventable by using correct SIR-Spheres microspheres doses and making allowances for dose reduction when there is increased risk of causing radiation damage such as in pre-existing liver damage, poor liver reserve or small volume tumour mass in the liver. The reported incidence of gastritis/duodenitis is <10%, while the reported rate of radiation induced liver disease is < 1%.

Rare complications that have been reported include acute pancreatitis resulting from SIR-Spheres microspheres refluxing back down the hepatic artery and lodging in the pancreas and liver abscess from infection of necrotic tumour. Previously reported radiation pneumonitis has not been observed where appropriate treatment workup and dose reductions are followed.

There is some evidence that there is a decrease in leucocyte levels, with a nadir eight weeks after implantation. This has been evident in both first line and refractory studies. The median number of leukocytes was $3.55 \times 10^9/L$ (NCIC CTC3 Grade 1). Leukocyte levels recover from this point, with the median value rising to normal levels 4-8 weeks after the decline.

² Unpublished data, Sirtex Technology Pty Ltd

CONFIDENTIAL

STUDY DEVICE: SIR-Spheres®

SCRI INNOVATIONS STUDY NUMBER: GI 189

DATE OF ORIGINAL PROTOCOL: 16 December 2013

Date of Amendment #1: 15 April 2014

Version 2.0

Please refer to the US Package Insert for detailed information on the risks associated with the use of SIR-Spheres microspheres.

8.2 Regorafenib

Regorafenib is to be administered in accordance with the recommendations in the approved labelling and in accordance with institutional standard of practice. Please refer to the US Package Insert http://labeling.bayerhealthcare.com/html/products/pi/Stivarga_PI.pdf for detailed information on how to prepare and administer Regorafenib.

8.2.1 Labeling, Packaging, and Supply

Regorafenib is commercially available and will be purchased by the patient or a third party.

8.2.2 Preparation and Administration of Regorafenib

A link to the full US Package Insert is provided in Section 8.2.

8.2.3 Precautions and Risks Associated with Regorafenib

Please refer to the US Package Insert for detailed information on the risks associated with the use of Regorafenib.

8.2.3.1 In-Vitro Radiosensitization Study of Regorafenib and Radiation in Adenocarcinoma Cell Lines

The radiosensitization of the Regorafenib / radiotherapy combination was evaluated in adenocarcinoma cell lines. The purpose of the study was to determine the extent to which Regorafenib would potentiate the tumoricidal effect of radiation. Colorectal adenocarcinoma cell lines were subjected to selected combinations of regorafenib concentrations and exposure to radiation. The addition of regorafenib to radiation did not enhance radiosensitization irrespective of the timing or temporal sequencing of the two agents. Moreover, there was no dose-dependent relationship observed in the radiosensitization of cancer cell lines. Based on the results of this study, Regorafenib is not an intrinsic radiosensitizer in colorectal cancer cells. A detailed report of study findings is included in Appendix H.

9. RESPONSE EVALUATIONS AND MEASUREMENTS

Response and progression will be evaluated in this study using the Response Evaluation Criteria in Solid Tumors (RECIST) Version 1.1 (see Appendix C). Lesions are either measurable or non-measurable according to the criteria. The term “evaluable” in reference to measurability will not be used, as it does not provide additional meaning or accuracy.

CONFIDENTIAL

STUDY DEVICE: SIR-Spheres®

SCRI INNOVATIONS STUDY NUMBER: GI 189

DATE OF ORIGINAL PROTOCOL: 16 December 2013

Date of Amendment #1: 15 April 2014

Version 2.0

10. STATISTICAL CONSIDERATIONS

10.1 Statistical Design

The safety of two treatment cohorts will be evaluated in this open-label study. The administration sequence of radioembolization with SIR-Spheres and regorafenib is different in the two treatment cohorts. The treatment cohorts are:

Cohort 1 Regorafenib (one cycle) followed by SIR-Spheres followed by re-initiation of regorafenib 2-4 weeks after SIR-Spheres

Cohort 2 SIR-Spheres followed by regorafenib to start 2-4 weeks after SIR-Spheres

Enrollment to Cohort 1 will be completed before Cohort 2 begins enrolling patients. All patients will take regorafenib, orally once-a-day, on Days 1-21 of a 28-day treatment cycle. Twenty-five patients will be treated in each cohort.

Primary Objective

The primary objective of the study is to evaluate the safety of two treatment cohorts combining regorafenib and SIR-Spheres in patients with refractory mCRC with liver metastasis.

Secondary Objectives

The secondary objectives of the study are to evaluate the overall response rate (ORR), progression free survival (PFS), and OS of patients with refractory mCRC when treated with combination SIR-Spheres and regorafenib in the two sequencing cohorts.

Exploratory Objectives

The exploratory objectives will evaluate the status of biomarkers and correlate the clinical outcomes of patients treated in the two SIR-Spheres and regorafenib cohorts.

10.2 Sample Size Considerations

There is no formal hypothesis testing in this study. The sample size of 50 patients (25 in each cohort) is based on clinical practicalities rather than statistical reasoning, in order to evaluate the safety of the 2 different sequences in treatment administration of SIR-Spheres microspheres and regorafenib.

With 25 patients per cohort, the 95% confidence interval for the response rate estimate would be no more than 21%.

10.3 Analysis Population

The following analysis populations will be used:

- Intent-To-Treat Population (ITT) is defined as all patients who have started study treatment (Radioembolization with SIR-Spheres ^{90}Y or regorafenib).
- Safety Population is defined as all patients who have received at least one dose of study treatment. In this instance, the ITT and safety populations would consist of the same patients.

CONFIDENTIAL

STUDY DEVICE: SIR-Spheres®

SCRI INNOVATIONS STUDY NUMBER: GI 189

DATE OF ORIGINAL PROTOCOL: 16 December 2013

Date of Amendment #1: 15 April 2014

Version 2.0

10.4 Data Analysis

Descriptive statistics, including mean, median, standard deviations and ranges for all continuous measures will be tabulated and reported. Percentages and frequencies for all categorical measures will also be presented. Time to events endpoints will be reported using Kaplan-Meier estimates, with 95% confidence intervals for median time to event.

10.4.1 Demographics and Baseline Characteristics

Demographic and baseline disease characteristics will be summarized for each cohort. Data to be tabulated will include demographic features such as age, sex and race, as well as disease-specific characteristics.

The number and percentages of patients screened, treated, completed the treatment/study and withdrawn from treatment/study for any reasons will be presented overall and also by cohort.

10.4.2 Efficacy Analysis

All efficacy analyses will be performed using the Intent-To-Treat Population.

- Overall Response Rate (ORR) is defined as the proportion of patients with observed CR or PR (i.e. 2 CRs or PRs at least 4 weeks apart) according to the RECIST 1.1 criteria.
- Progression Free Survival (PFS), defined as the time from the first day of study drug administration (Day 1) to disease progression as defined by the RECIST v1.1 criteria, or death on study. Patients who are alive and free from disease progression will be censored at the date of last adequate tumor assessment.
- Overall Survival (OS), defined as the time from the first day of study drug administration (Day 1) to death. Patients who are alive will be censored at the date of last known date alive.

For ORR, the estimates and the associated 95% confidence interval (based on the Clopper-Pearson method) in each treatment group will be calculated.

For PFS and OS, Kaplan-Meier curves will be generated and the median time to event and the associated 95% confidence interval will be provided.

10.4.3 Early Safety Monitoring and Stopping Rules

A safety review for toxicity by the Medical Monitor will occur after the first 10 patients have been enrolled in each cohort and treated with one cycle of regorafenib and SIR-spheres (combination therapy) to assess the frequency of \geq Grade 3 adverse events and all SAEs. Accrual will not be halted while the analysis is being conducted.

Stopping Rules Due to Toxicities of Combination Therapy

Stopping rules due to toxicities assessed as related to combination therapy by the Medical Monitor will be defined as follows:

- A patient death considered to be caused by AEs of combination therapy

CONFIDENTIAL

STUDY DEVICE: SIR-Spheres®

DATE OF ORIGINAL PROTOCOL: 16 December 2013

Date of Amendment #1: 15 April 2014

SCRI INNOVATIONS STUDY NUMBER: GI 189

Version 2.0

- A patient with Grade 4 AST, ALT, or irreversible hepatic failure assessed as related to combination therapy;
- More than 2 patients that develop Grade 3 AST, ALT, or total bilirubin assessed as related to combination therapy;
- More than 2 patients develop Grade 3 bleeding in the lung, stomach, small intestine, or liver assessed as related to combination therapy.

If the early stopping rules are met or safety signals emerge from the group of the first 10 patients treated with combination therapy in each cohort, patient recruitment will discontinue and the study will be reassessed. Any outcome of these safety reviews will be communicated in a timely manner to the participating investigators so that they may notify their IRBs.

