6.2 Regorafenib Dose Modifications for Non-Hematologic Toxicity

6.2.1 Regorafenib Dose Modifications for Abnormal Liver Function Tests

Regorafenib has been associated with severe drug-induced liver injury with fatal outcome in previous studies. Liver function tests (LFTs) will be monitored during study treatment as described in **Error! Reference source not found.** Appendix A and **Error! Reference source not found.** Appendix B. Dose modifications for regorafenib are recorded in Table 3 below.

Table 3 Regorafenib Dose Modifications for Abnormal Liver Function Tests

Toxicity	Regorafenib Dose
Baseline - Grade 1 And Recurrence OR Baseline Grade 1 – Grade 2 And Recurrence	Treat on time and check AST, ALT and bilirubin 2x/week for 2 weeks followed by weekly assessments for at least 4 weeks.
Baseline - Grade 2	Hold dose until \leq Grade 1 and check AST, ALT and bilirubin 2x/week. Resume regorafenib at 1 lower dose level and check AST, ALT, bilirubin 2x/week for 2 weeks followed by weekly assessments for at least 4 weeks. ^a
Recurrence of Baseline - Grade 2	Discontinue regorafenib ^b .
Baseline Any Grade-Grade 3	Hold dose until \leq Grade 1 for baseline - Grade 1 OR until Grade 2 if baseline was Grade 2.

CONFIDENTIAL

STUDY DEVICE: SIR-Spheres®

SCRI INNOVATIONS STUDY NUMBER: GI 189

DATE OF ORIGINAL PROTOCOL: 16 December 2013

Version 2.0

Date of Amendment #1: 15 April 2014

	Check AST, ALT and bilirubin 2x/week.
	Resume regorafenib at 1 lower dose level and check AST, ALT, bilirubin 2x/week for 2 weeks followed by weekly assessments for at least 4 weeks. ^a
	Note: If ALT or AST >8 x ULN with a concomitant rise in bilirubin (of any degree) compared to previous bilirubin values, consider permanent discontinuation at the first occurrence ^b .
Recurrence of Baseline Any Grade-Grade 3	Discontinue regorafenib ^b .
Baseline Any Grade-Grade 4	Discontinue regorafenib ^b

^a If all values remain stable for 2 full cycles, dose re-escalation may be considered at the discretion of the investigator. After re-escalation AST, ALT, and bilirubin should be checked 2x/week for 2 weeks, followed by weekly assessments for at least 4 weeks.

^b In case of discontinuation, AST, ALT, and bilirubin should be checked 2x/week for 2 weeks, followed by weekly assessments until recovery to baseline.

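### One or two related Grade 4 bilirubin rises or non-fatal Grade 4 bleeds meet no listed stopping rule on their own, although a single Grade 4 AST or ALT does

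*Protocol*

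**What the plan says.** Protocol Sections 5 and 10.4.3 carry the same four rules. All depend on the Medical Monitor attributing the event to combination therapy.

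1. One death caused by the combination.
2. One patient on the liver rule: "A patient with Grade 4 AST, ALT, or irreversible hepatic failure assessed as related to combination therapy".
3. A liver count rule: "More than 2 patients that develop Grade 3 AST, ALT, or total bilirubin assessed as related to combination therapy".
4. A bleeding count rule: "More than 2 patients develop Grade 3 bleeding in the lung, stomach, small intestine, or liver assessed as related to combination therapy".

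The consequence has two limbs. It begins "If the early stopping rules are met or safety signals emerge from the group of the first 10 patients treated with combination therapy", applied to each cohort, and the action is that "patient recruitment will discontinue and the study will be reassessed". Nothing defines a safety signal. The Medical Monitor's review after ten patients per cohort covers AEs at or above the grade in "Grade 3 adverse events and all SAEs". The protocol prints a greater-than-or-equal sign before that grade. The two count rules have no such sign.

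Safety is the primary objective. SAP Section 1.4 ticks a safety review and leaves the independent DMC/DSMB box empty.

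**The concern.** The list treats events of the same grade differently. One related Grade 4 transaminase rise stops recruitment automatically. One related Grade 4 bilirubin rise, or one related Grade 4 bleed that the patient survives, does not; nor do two. The count rules do not clearly cover these cases either, because they name Grade 3 where the review a few lines earlier names Grade 3 or higher.

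At stake is whether the written rules act predictably in a study whose main purpose is safety. The sponsor chose to fix triggers in advance for some Grade 4 events. For bilirubin and bleeding the same seriousness is left to discretion, with no stated reason for the difference.

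**Working it through.** The protocol states no operating characteristics for these rules, so there is no planned figure to reproduce. The check has two parts.

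**Step 1: events set against the rules.** Each event is taken as related to combination therapy, without irreversible hepatic failure and without death. The literal column counts each patient only at the highest grade reached.

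| Event in the first ten patients | Grade 3 read literally | Read as Grade 3 or higher |
|---|---|---|
| 1 Grade 4 AST or ALT | rule 2 met | rule 2 met |
| 1 or 2 Grade 4 bilirubin | none | none |
| 3 Grade 4 bilirubin | none | rule 3 met |
| 1 or 2 Grade 4 bleeds | none | none |
| 3 Grade 4 bleeds (named sites) | none | rule 4 met |
| 2 Grade 3 liver tests + 1 Grade 4 bilirubin | none | rule 3 met |
| 2 Grade 4 bilirubin + 2 Grade 4 bleeds | none | none |

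The result for one or two cases alone is the same on both readings. The reading matters once the count could reach three.

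**Step 2: how often the gap could arise.** Inputs:

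- n = 10 patients per cohort (Section 10.4.3).
- p4, the rate of related Grade 4 bilirubin: an assumption. The nearest figure in the documents is Section 8.1.3, which puts radiation-induced liver disease below 1%, with no grade. I use 0.1%, 0.5% and 1%.
- p3, the rate of related Grade 3 AST, ALT or bilirubin pooled: an assumption, 10%, with 5% and 20% as alternatives.

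The chance of at least one Grade 4 case is 1 − (1 − p4)^10. This is also the chance that a single-patient rule would fire:

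- p4 = 1%: 1 − 0.99^10 = 9.6%
- p4 = 0.5%: 1 − 0.995^10 = 4.9%
- p4 = 0.1%: 1 − 0.999^10 = 1.0%

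The chance that a Grade 4 case occurs and the count rule is still unmet uses the reading more favourable to the plan (Grade 3 or higher). With q = 1 − p3 − p4 it is

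10·p4·q^9 + 90·p3·p4·q^8 + 45·p4²·q^8.

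At p3 = 10% and p4 = 1%, q = 0.89 and the terms are 0.0350 + 0.0354 + 0.0018 = 7.2%. At p4 = 0.5% the result is 3.7%, and at 0.1% it is 0.8%. With p4 held at 1%, it is 8.7% for p3 = 5% and 4.0% for p3 = 20%. For Grade 4 AST or ALT the corresponding figure is zero, because one case is enough.

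These gap figures leave out the other listed rules and the safety-signals limb, so they are upper bounds on the pauses that the bilirubin rule would add. The same formula serves for bleeding if p3 and p4 are the Grade 3 and Grade 4 rates at the four sites; the documents give neither. A combination rate above 1% cannot be excluded, since regorafenib carries its own liver risk, but the documents offer no number. At a purely illustrative 2%, at least one case would occur in 18.3% of ten-patient groups.

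**The case against.** The strongest reply is that a route to stopping already exists. The safety-signals limb can halt recruitment. The Medical Monitor sees every AE of Grade 3 or higher and every SAE. A life-threatening AE is an SAE, reportable within 24 hours (Sections 11.1.2 and 11.2). Treatment may not be given until liver function again meets the entry criteria, which include bilirubin (Sections 7.3.5, 7.3.7 and 7.4.4). SAEs go to the device manufacturer for a relationship decision within 72 hours (Section 11.4). Since every listed rule also needs the Medical Monitor's attribution, the change partly swaps one judgement by that person for another. All of this stands, and it makes the gap small. It does not close it: the safety-signals limb has no criteria, whereas a related Grade 4 AST needs no further decision.

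Three stronger readings are tempting but not supported.

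- A reader might infer that Table 3 in Section 6.2.1 contradicts the rules, because its row "Baseline Any Grade-Grade 4" discontinues regorafenib without separating bilirubin from transaminases. That table governs dosing of one patient. It also discontinues the drug for some recurrent Grade 2 and for recurrent Grade 3 liver tests, which nobody would make single-patient study stops. Different thresholds at the two levels are not a contradiction.
- A reader might infer from Section 8.1.3 that the rules miss the device's typical liver injury, since radioembolization-induced liver disease is described as raised bilirubin with little transaminase change. The section gives a level above 3 mg/dL and no grade. It does not show that typical cases reach Grade 4, or that a Grade 4 trigger would catch them. Bilirubin is already in the Grade 3 count rule.
- A reader might infer that, read literally, no number of Grade 4 cases could ever stop the study. A patient recorded at Grade 3 on the way to Grade 4 has arguably developed Grade 3, and Section 11.3.2 records changes in severity separately. The safe statement is that Grade 4 cases may not count.

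**Conclusion.** The gap follows from the rule text and does not depend on any assumed rate. One or two related Grade 4 bilirubin rises without irreversible hepatic failure, or one or two related non-fatal Grade 4 bleeds, meet no listed rule on their own under either reading of Grade 3. A bilirubin case that becomes irreversible hepatic failure meets rule 2, and a bleed that causes death meets rule 1. On the wider reading, such cases can also combine with Grade 3 cases to reach three.

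At an assumed 1% rate the bilirubin gap would arise in roughly 4% to 9% of ten-patient groups, depending on the assumed Grade 3 rate, and in fewer at lower rates. Those figures rest on assumed rates and on patients being independent.

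The unticked DMC/DSMB box might suggest that the trial is unmonitored. The documents do not support that: a Medical Monitor review, SAE reporting and a discretionary stop are all in place. This is a minor, partly mitigated gap in the listed rules, worth correcting because the correction is short.

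**What to change.** In both Section 5 and Section 10.4.3:

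- Write ≥ Grade 3 in the liver count rule and in the bleeding count rule, matching the grade range of the safety review.
- Add related Grade 4 total bilirubin, and related Grade 4 bleeding at the four sites already named, to the single-patient rule.

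The change needs no extra patients, visits or tests. Its cost is more recruitment pauses. Each added single-patient rule would fire in at most about 9.6% of ten-patient groups at a true 1% rate, 4.9% at 0.5% and 1.0% at 0.1%. If both events ran at 1% independently, at least one added rule would fire in 1 − 0.99^20 = 18.2% of ten-patient groups, and in 1 − 0.99^40 = 33.1% of trials counting the first ten patients of both cohorts. Some of those pauses would have happened anyway under the count rules or the safety-signals limb. If the sponsor applied the bilirubin rule to all 25 patients in a cohort, it would fire in 1 − 0.99^25 = 22.2% of cohorts at 1%. A pause leads to reassessment and does not in itself end the study.

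If the sponsor prefers to keep Grade 4 bilirubin and bleeding discretionary, one sentence saying so, with the reason, would remove the ambiguity.
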